7.2.2. Exclusion criteria

Patients meeting any of the following criteria will not be included in the study:

1. Having a diagnosis of valvular atrial fibrillation, post-operative atrial fibrillation, rheumatic atrial fibrillation or mechanical-valvular atrial fibrillation during the baseline and post-index period
2. Having a cardiac surgery procedure record during the baseline period
3. Having a joint replacement procedure record during the baseline period
4. Having a procedure of prosthetic heart valve during the baseline period
5. Having a diagnosis of venous thromboembolism during the baseline period
6. Female patients with pregnancy during the follow-up period
7. Patients prescribed “off-label” doses of OACs (per Japanese package insert of each OAC) or patients treated with OAC but in “off-label” or “contraindicated” manners.

7.3. Variables

Demographic and clinical characteristics are collected during the baseline period or at the index date.

Table 1: Demographic and clinical information of patients

<Eliquis>

<B0661120> Safety and effectiveness evaluation of patients with non-valvular atrial fibrillation treated with OACs: Comparison between NOACs and warfarin (CER3)

<Final ver.1.1><20180508>

Variable	Obtained from	Operational definition
Sex Category	Index date	Dichotomous variable equals 1 if sex is male and 2 if female
Age	Index date	Age (in years) at the index date
Physician specialty	Index date	Dichotomous variable equals 1 if a physician specialty on the index date is categorized into a cardiac specialty and 0 if others. Following specialties will be categorized as the cardiac specialty: cardiology stroke, cardiovascular surgery, pediatric cardiology, neurosurgery, cardiovascular medicine, and neurology. If there are ≥1 specialties but including the cardiac specialty, the physician specialty will be regarded as the cardiac specialty.
Hospital size (<500 beds or not)	Index date	Dichotomous variable equals 1 if hospital size on the index date is <500 beds and 0 if ≥500 beds.
Hospitalization status on index date	Index date	Dichotomous variable equals 1 if hospitalization status is inpatient and 0 if outpatient.
CHADS ₂	Baseline period	CHADS ₂ score will be calculated based on age and the presence of congestive heart failure, hypertension, diabetes, and stroke or TIA.
CHA ₂ DS ₂ -VASC	Baseline period	Score calculated by appointing 1 point each for congestive heart failure/left ventricle dysfunction, hypertension, diabetes, vascular disease (prior MI, peripheral arterial disease, or aortic plaque), age between 65-74, female gender; and 2 points each for age >75 years and prior stroke, TIA, or thromboembolism.
PT-INR (Prothrombin time-international normalized ratio)	Baseline period	Continuous variable. * Only available for patients treated with warfarin
Heart failure diagnosis in baseline	Baseline period	Dichotomous variable equals 1 if there are ≥1 diagnoses for heart failure ICD-10 or disease codes during the baseline period.
Coronary heart disease diagnosis in baseline	Baseline period	Dichotomous variable equals 1 if there are ≥1 diagnoses for coronary heart disease ICD-10 or disease codes during the baseline period.
Peripheral arterial disorder diagnosis in baseline	Baseline period	Dichotomous variable equals 1 if there are ≥1 diagnoses for peripheral arterial disorder ICD-10 or disease codes during the baseline period.
Myocardial infarction diagnosis in baseline	Baseline period	Dichotomous variable equals 1 if there are ≥1 diagnoses for myocardial infarction ICD-10 or disease codes during the baseline period.
Hyperthyroidism or thyrotoxicosis in baseline	Baseline period	Dichotomous variable equals 1 if there are ≥1 diagnoses for hyperthyroidism ICD-10 or disease codes during the baseline period.
Stroke, TIA or SE diagnosis in baseline	Baseline period	Dichotomous variable equals 1 if there are ≥1 diagnoses for Stroke, TIA or systemic embolism ICD-10 or disease codes during the baseline period.
Renal dysfunction diagnosis in baseline	Baseline period	Dichotomous variable equals 1 if there are ≥1 diagnoses for renal dysfunction ICD-10 or disease codes during the baseline period.
Liver dysfunction diagnosis in baseline	Baseline period	Dichotomous variable equals 1 if there are ≥1 diagnoses for liver dysfunction ICD-10 or disease codes during the baseline period.
Bleeding diagnosis in baseline	Baseline period	Dichotomous variable equals 1 if there are ≥1 diagnoses for bleeding ICD-10 or disease codes during the baseline period.
Hypertension diagnosis in baseline	Baseline period	Dichotomous variable equals 1 if there are ≥1 diagnoses for hyper tension ICD-10 or disease codes during the baseline period.
Diabetes mellitus diagnosis in baseline	Baseline period	Dichotomous variable equals 1 if there are ≥1 diagnoses for diabetes mellitus ICD-10 or disease codes during the baseline period.

<Eliquis>

<B0661120> Safety and effectiveness evaluation of patients with non-valvular atrial fibrillation treated with OACs: Comparison between NOACs and warfarin (CER3)

<Final ver.1.1><20180508>

Cancer diagnosis in baseline	Baseline period	Dichotomous variable equals 1 if there are ≥ 1 diagnoses for diabetes mellitus ICD-10 or disease codes during the baseline period.
Treated with antiplatelet drug in baseline	Baseline period	Dichotomous variable equals 1 if there are ≥ 1 prescriptions of antiplatelet drug ATC or receipt codes during the baseline period.
Treated with NSAIDs in baseline	Baseline period	Dichotomous variable equals 1 if there are ≥ 1 prescriptions of NSAIDs ATC or receipt codes during the baseline period.
Treated with gastric secretion inhibitor in baseline	Baseline period	Dichotomous variable equals 1 if there are ≥ 1 prescriptions of gastric secretion inhibitor drug ATC or receipt codes during the baseline period.
Treated with statin-based drug in baseline	Baseline period	Dichotomous variable equals 1 if there are ≥ 1 prescriptions of statin-based drug ATC or receipt codes during the baseline period.
Treated with anti-hypertensives in baseline	Baseline period	Dichotomous variable equals 1 if there are ≥ 1 prescriptions of anti-hypertensive ATC or receipt codes during the baseline period.
Treated with anti-arrhythmics in baseline	Baseline period	Dichotomous variable equals 1 if there are ≥ 1 prescriptions of anti-arrhythmics ATC or receipt codes during the baseline period.
Treated with beta-blockers in baseline	Baseline period	Dichotomous variable equals 1 if there are ≥ 1 prescriptions of beta-blockers ATC or receipt codes during the baseline period.
Treated with heparins in baseline	Baseline period	Dichotomous variable equals 1 if there are ≥ 1 prescriptions of heparins ATC or receipt codes during the baseline period.
Cardioversion in baseline	Baseline period	Dichotomous variable equals 1 if there is ≥ 1 operation of cardioversion receipt codes during the baseline period.
Major bleeding in follow-up	Follow-up period	Dichotomous variable equals 1 if there are ≥ 1 diagnoses for major bleeding ICD-10 or disease codes during the follow-up period.
Any bleeding in follow-up	Follow-up period	Dichotomous variable equals 1 if there are ≥ 1 diagnoses for any bleeding ICD-10 or disease codes during the follow-up period.
Stroke/SE in follow-up	Follow-up period	Dichotomous variable equals 1 if there are ≥ 1 diagnoses for stroke or SE ICD-10 or disease codes during the follow-up period.

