7.5. Study size

All eligible patients are extracted from the database and used for the analysis. In the previous study (CER2; conducted based on the data from March 1st, 2011 to December 31st, 2017 for apixaban, edoxaban and warfarin), 14,830 patients on warfarin, 16,176 patients on apixaban and 4,438 patients on edoxaban were eligible for the analysis. The required number of patients for the planned analysis and the estimated number of eligible patients for each cohort is shown in a Statistical Analysis Plan

<Eliquis>

<B0661120> Safety and effectiveness evaluation of patients with non-valvular atrial fibrillation treated with OACs: Comparison between NOACs and warfarin (CER3)

<Final ver.1.1><20180508>

(SAP).

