8.4 COVARIATES

We will use demographic and clinical information available at the index date and baseline period of the initiation prescription for apixaban, edoxaban, and warfarin cohorts.

Variable	Role	Operational definition
Sex Category	Baseline characteristic	Dichotomous variable equals 1 if sex is male and 2 if female
Age	Baseline characteristic	Age (in years) at the index date
Physician specialty	Baseline characteristic	Dichotomous variable equals 1 if a physician specialty on the index date is categorized into a cardiac specialty and 0 if others. Following specialties will be categorized as the cardiac specialty: cardiology stroke, cardiovascular surgery, pediatric cardiology, neurosurgery, cardiovascular medicine, and neurology. If there are ≥ 1 specialties but including the cardiac specialty, the physician specialty will be regarded as the cardiac specialty.
Hospital size (<500 beds or not)	Baseline characteristic	Dichotomous variable equals 1 if hospital size on the index date is <500 beds and 0 if ≥ 500 beds.
Hospitalization status on index date	Baseline characteristic	Dichotomous variable equals 1 if hospitalization status is inpatient and 0 if outpatient.
CHADS ₂	Baseline characteristic	CHADS ₂ score will be calculated based on age and the presence of congestive heart failure, hypertension, diabetes, and stroke or TIA.

CHA ₂ DS ₂ -VASC	Baseline characteristic	CHA ₂ DS ₂ -VASC score will be calculated based on age and the presence of congestive heart failure, hypertension, diabetes, stroke or TIA, vascular disease and sex category.
PT-INR (Prothrombin time-international normalized ratio)	Baseline period	Continuous variable. * Only available for patients treated with warfarin
Heart failure diagnosis in baseline	Baseline characteristic	Dichotomous variable equals 1 if there are ≥ 1 diagnoses for heart failure ICD-10 or disease codes during the baseline period.
Coronary heart disease diagnosis in baseline	Baseline characteristic	Dichotomous variable equals 1 if there are ≥ 1 diagnoses for coronary heart disease ICD-10 or disease codes during the baseline period.
Peripheral arterial disorder diagnosis in baseline	Baseline characteristic	Dichotomous variable equals 1 if there are ≥ 1 diagnoses for peripheral arterial disorder ICD-10 or disease codes during the baseline period.

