10 STATISTICAL METHODOLOGY AND STATISTICAL ANALYSES

10.1 STATISTICAL METHODS

10.1.1 Propensity Score Matching

In this study, matched cohorts (apixaban vs. warfarin, dabigatran versus warfarin, edoxaban vs. warfarin and rivaroxaban versus warfarin) will be created. Propensity scores will be estimated by unconditional logistic regression analyses that incorporate potential predictors of therapy as independent variables in the regression and cohort status as the outcome. The matching between warfarin group and each NOAC group (reference), 1:1 propensity score matching (PSM) method without replacement will be conducted. We will apply nearest neighbour method within caliper (width=0.2 times the standard deviation of the logit of the propensity score) matching technique. Standardized differences will be used to assess the balance of covariate between warfarin group and each NOAC group. If the standardized difference is less than 10%, the covariates are considered balanced. The following covariates will be included in the logistic regression:

- age on index date
- gender

- CHADS₂ score in baseline
- CHA₂DS₂-VASc score in baseline
- heart failure diagnosis in baseline
- coronary heart disease diagnosis in baseline
- peripheral arterial disorder diagnosis in baseline
- myocardial infarction diagnosis in baseline
- hyperthyroidism or thyrotoxicosis in baseline
- TIA diagnosis in baseline
- stroke or SE diagnosis in baseline
- renal dysfunction diagnosis in baseline
- liver dysfunction diagnosis in baseline
- bleeding diagnosis in baseline
- hypertension diagnosis in baseline
- diabetes mellitus diagnosis in baseline
- treated with antiplatelet drug in baseline
- treated with NSAIDs in baseline
- treated with gastric secretion inhibitor in baseline
- treated with statin-based drug in baseline
- treated with anti-hypertensives in baseline
- treated with anti-arrhythmics in baseline
- treated with beta-blockers in baseline
- treated with heparins in baseline
- cardioversion in baseline

The operational definitions for the above covariates are shown in the Section 6.4.

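### The CHA₂DS₂-VASc age bands in Protocol Table 1 skip age 75, and the SAP gives no cut-points that would repair them

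*Protocol*

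**What the plan says.** **Scoring rule.** Protocol Section 7.3, Table 1, is the only place in either document that gives age points for CHA₂DS₂-VASc. Its list of one-point items ends, and its two-point items follow, with these words: "age between 65-74, female gender; and 2 points each for age >75 years and prior stroke, TIA, or thromboembolism". The same table defines age as "Age (in years) at the index date".

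**SAP definition.** SAP Section 8.4 says that the "score will be calculated based on age and the presence of congestive heart failure, hypertension, diabetes, stroke or TIA, vascular disease and sex category". It gives no bands and no points. Prior thromboembolism, which earns points in the protocol, is not in this list.

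**Where the score is used.**
- SAP Section 10.1.1 includes "CHA₂DS₂-VASc score in baseline" in the logistic model for the propensity score, alongside "age on index date" and separate terms for sex and most of the component diagnoses.
- SAP Section 10.1.2 refers back to 10.1.1 for the propensity score behind the stabilized weights.
- The balance criterion is: "If the standardized difference is less than 10%, the covariates are considered balanced". Under SAP Section 10.1.3, a variable that fails it is added to the Cox model.
- Protocol Table 1 and SAP 8.4 both list the score as a baseline variable.

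**The concern.** A stroke-risk score that awards points for age should not fall as age rises. Under the written bands a 75-year-old scores lower on age than a 65-year-old, and then gains 2 points on turning 76. A programmer who follows the protocol would produce that result, and a code check against the protocol would pass it.

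The main thing at stake is the reported baseline table. Readers will use the mean and distribution of the score to judge stroke risk in each cohort and to compare the cohorts with those of other studies. The second is the propensity model, which would carry a mis-scored covariate in all four comparisons, under both matching and weighting.

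**Working it through.** The plan states no figure on this point, so there is none to reproduce. The check applies the written rule age by age and then sizes the effect under stated assumptions.

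**1. Age points by age, in completed years**

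Rule as written: 1 point if 65 ≤ age ≤ 74; 2 points if age > 75; otherwise 0. Contiguous rule: the same, with the upper band starting at age ≥ 75.

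| Age | As written | Upper band from 75 |
|---|---|---|
| 64 | 0 | 0 |
| 65 | 1 | 1 |
| 74 | 1 | 1 |
| 75 | 0 | 2 |
| 76 | 2 | 2 |
| 80 | 2 | 2 |

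Of the ages checked, only 75 differs, and it differs by 2 points.

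**2. If age were held with decimals**

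The protocol says years, not completed years. With decimals, the written rule gives 0 points to everyone above 74 and up to and including 75. At 74.5, for example, the rule gives 0, and it still gives 0 after the upper band is moved to ≥ 75. The gap exists on either reading. The one-character repair closes it fully only if age is in completed years.

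**3. Effect on the mean score**

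Mean shift = 2 × share of patients aged 75. The documents do not give this share; 2% to 5% is an assumption.

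- 2 × 0.02 = 0.04 points too low
- 2 × 0.05 = 0.10 points too low

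For scale only, Protocol Section 7.5 reports from an earlier study that "14,830 patients on warfarin, 16,176 patients on apixaban and 4,438 patients on edoxaban were eligible for the analysis". At that size the warfarin cohort would have 14,830 × 0.02 ≈ 297 to 14,830 × 0.05 ≈ 742 mis-scored patients, and the apixaban cohort 16,176 × 0.02 ≈ 324 to 16,176 × 0.05 ≈ 809.

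**4. Effect on the balance check**

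Only a difference between cohorts in the share aged 75 can move the standardized difference. To first order, holding the SD fixed:

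change in % = 100 × 2 × (difference in share) ÷ SD of the score.

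Both inputs are assumptions: a difference in share of 0.5 to 2 percentage points, and an SD of 1.3 to 1.8.

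- Smallest: 100 × 2 × 0.005 ÷ 1.8 ≈ 0.6%
- Middle: 100 × 2 × 0.01 ÷ 1.5 ≈ 1.3%
- Largest: 100 × 2 × 0.02 ÷ 1.3 ≈ 3.1%

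The threshold is 10%. On these inputs the gap alone would not decide whether the score counts as balanced, unless it were already close to the limit.

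**5. Effect on the hazard ratios**

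This was not calculated; it would need patient data. The reasoning is that one year of age is affected, the same rule serves every cohort, and the propensity model already holds age, sex, CHADS₂, heart failure, hypertension, diabetes, myocardial infarction, peripheral arterial disorder, TIA, and stroke or SE as separate terms. The mis-scored part therefore adds very little.

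**The case against.** Four points can be made on the other side.

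**The score may never be wrong in practice.** Protocol Section 7.7 leaves detailed methodology to the SAP and lets the SAP modify the protocol. The SAP does not repeat the >75 wording, so an analyst could well start the upper band at 75. This stands, and it is why the point is conditional on Table 1 being programmed as written. A reader might infer that the study's score is in fact wrong; the documents do not show that. But silence in the SAP is not a correction. SAP 10.1.1 does not help either: it points to a Section 6.4 for the covariate definitions, whereas they are in Section 8.4.

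**The sign may be a PDF-reading loss.** A ≥ set as an underlined > could lose its underline, and inequality signs are used loosely elsewhere, as in the discontinuation and switching rules of Protocol Section 7.2. This cannot be excluded. It is unlikely, because ≥ survives in the same table in the hospital-size and diagnosis rows.

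**The consequence is small.** This stands in full. A reader might infer that a covariate falling at age 75 distorts confounding control in the oldest patients. The documents do not support that, because age and the main components are separate terms in the model.

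**The thromboembolism difference may be shorthand.** The SAP entry is a short component list without points, so it may be a summary and not a different rule. Its reach is also limited: baseline venous thromboembolism is an exclusion, and stroke or SE is its own propensity covariate. It is a secondary item to reconcile, not evidence that the score was deliberately redefined.

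**Conclusion.** The bands in Protocol Table 1 are not contiguous, and nothing else in the documents closes the gap. Followed literally with age in completed years, the rule scores every 75-year-old 2 age points below a band starting at 75, and below patients aged 65 to 74. That would make the reported baseline score and one propensity covariate wrong for those patients.

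The understatement of the mean, about 0.04 to 0.10 points, rests on the assumed 2% to 5% share aged 75. The movement of about 0.6% to 3.1% in the standardized difference rests on assumed differences in that share and assumed SDs. The expected effect on the hazard ratios is negligible.

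This is a definition to correct before programming. It is not a threat to the main comparisons, and the documents do not show that any score has been miscalculated.

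**What to change.** - In Protocol Table 1, change >75 to ≥75 for the two-point age band, and say that age is in completed years so that 65 to 74 and ≥75 meet without a gap.
- In SAP 8.4, state the same bands and the points for every component, so that the programming document carries the rule.
- In the same edit, settle whether prior thromboembolism earns points, and make the two component lists agree.
- CHADS₂ is also a propensity covariate and has no age cut-point in either document; its scoring rule can be written out at the same time.
- Correct the cross-reference in SAP 10.1.1 from Section 6.4 to Section 8.4.

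The cost is one character and a short phrase in the protocol and a few lines in the SAP. No analysis method, sample or endpoint changes. If programming has already been done, check which cut-point the code uses and record it.

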Myocardial infarction diagnosis in baseline	Baseline characteristic	Dichotomous variable equals 1 if there are ≥ 1 diagnoses for myocardial infarction ICD-10 or disease codes during the baseline period.
Hyperthyroidism or thyrotoxicosis in baseline	Baseline characteristic	Dichotomous variable equals 1 if there are ≥ 1 diagnoses for hyperthyroidism ICD-10 or disease codes during the baseline period.
Stroke, TIA or SE diagnosis in baseline	Baseline characteristic	Dichotomous variable equals 1 if there are ≥ 1 diagnoses for Stroke, TIA or systemic embolism ICD-10 or disease codes during the baseline period.
Renal dysfunction diagnosis in baseline	Baseline characteristic	Dichotomous variable equals 1 if there are ≥ 1 diagnoses for renal dysfunction ICD-10 or disease codes during the baseline period.
Liver dysfunction diagnosis in baseline	Baseline characteristic	Dichotomous variable equals 1 if there are ≥ 1 diagnoses for liver dysfunction ICD-10 or disease codes during the baseline period.
Bleeding diagnosis in baseline	Baseline characteristic	Dichotomous variable equals 1 if there are ≥ 1 diagnoses for bleeding ICD-10 or disease codes during the baseline period.
Hypertension diagnosis in baseline	Baseline characteristic	Dichotomous variable equals 1 if there are ≥ 1 diagnoses for hyper tension ICD-10 or disease codes during the baseline period.
Diabetes mellitus diagnosis in baseline	Baseline characteristic	Dichotomous variable equals 1 if there are ≥ 1 diagnoses for diabetes mellitus ICD-10 or disease codes during the baseline period.
Cancer diagnosis in baseline	Baseline period	Dichotomous variable equals 1 if there are ≥ 1 diagnoses for diabetes mellitus ICD-10 or disease codes during the baseline period.
Treated with antiplatelet drug in baseline	Baseline characteristic	Dichotomous variable equals 1 if there are ≥ 1 prescriptions of antiplatelet drug ATC or receipt codes during the baseline period.
Treated with NSAIDs in baseline	Baseline characteristic	Dichotomous variable equals 1 if there are ≥ 1 prescriptions of NSAIDs ATC or receipt codes during the baseline period.

Treated with gastric secretion inhibitor in baseline	Baseline characteristic	Dichotomous variable equals 1 if there are ≥ 1 prescriptions of gastric secretion inhibitor drug ATC or receipt codes during the baseline period.

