10.1.3 Analysis of Time-to-Event Data

Time-to-endpoints will be summarized by OAC with the number and percentage of patients with event, and event rates. Event rates will be calculated as the number of patients with event per 100 patient-years at risk. In addition, total patient-years will be presented for each OAC.

Patients who experience a clinical endpoint event after the earlier of their discontinuation of the index OAC, switching from the index OAC, withdrawal from the database, or the end of intended follow-up period (i.e., two years after the index date as primary and one year for a sensitive analysis) will be censored.

Patients who do not experience a clinical endpoint event will be censored at the earlier of their discontinuation of the index OAC, switching from the index OAC or withdrawal from the database will be censored.

Propensity score matching

See above

Cox proportional hazards model

Cox proportional hazards model will be used to compare endpoints in each of the propensity-score-matched cohorts, with robust sandwich estimates to account for the clustering within matched sets. The Cox proportional hazards model will include only index OAC treatment as the independent variable if patient characteristics are balanced between groups based on standardized difference in components of the PS. If not balanced, the unbalanced variable will be also included to the model in addition to the index OAC treatment. The hazard ratios with corresponding 95% confidence intervals and p-values will be reported.

CCI

Kaplan-Meier Method

For each endpoint, Kaplan-Meier curves will be plotted for the time from the index date to first event by index OAC treatment in each of the propensity-score-matched cohorts. The log-rank test is used for comparison between two curves.

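### The baseline cancer variable carries the diabetes definition in both documents and contradicts the SAP's own cancer code list; the baseline table and balance check are affected, the hazard ratios are not

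*Protocol*

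**What the plan says.** Protocol 7.3, Table 1, lists diabetes and cancer as two separate baseline variables. The diabetes rule is "Dichotomous variable equals 1 if there are ≥1 diagnoses for diabetes mellitus ICD-10 or disease codes during the baseline period". The cancer row has the same sentence; the only difference is a space after the inequality sign.

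SAP 8.4 again has a separate row labelled "Cancer diagnosis in baseline", and its operational definition is "Dichotomous variable equals 1 if there are ≥ 1 diagnoses for diabetes mellitus ICD-10 or disease codes during the baseline period". The diabetes row just above it has the identical sentence.

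SAP Appendix-1 treats the two conditions differently. Diabetes has codes E10 to E14. Cancer has its own list, which runs from C00 to C97 and from D00 to D48 with gaps. The cancer row in SAP 8.4 has no pointer to this list.

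The propensity model in SAP 10.1.1 includes "diabetes mellitus diagnosis in baseline" but not cancer. The balance criterion there is "If the standardized difference is less than 10%, the covariates are considered balanced". SAP 10.1.3 keeps the Cox model to treatment alone "if patient characteristics are balanced between groups based on standardized difference in components of the PS", and otherwise adds the unbalanced variable.

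**The concern.** A variable labelled cancer that is built from diabetes codes says nothing about cancer. The error stands in both documents in complete sentences, so it is neither a text-extraction fault nor a redaction. A programmer who follows the operational definition produces two identical lines in the baseline table, one of them mislabelled.

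What is at stake is the check on comparability. Protocol 7.9 acknowledges that patients on different treatments may not be comparable and that differences left out of the matching score may still affect the results. Cancer is one of the characteristics the plan chose to record but left out of the score, so the baseline comparison is the only disclosed place where an imbalance in it could be seen. If that line really shows diabetes, which the score does include, it will tend to look reassuring after matching whatever the true distribution of cancer.

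**Working it through.** The plan states no figure on this point, so there is none to reproduce. The check is a comparison of the texts, followed by an illustration of size.

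**1. The texts side by side**

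| Place | Diabetes | Cancer |
|---|---|---|
| Protocol 7.3, Table 1 | diabetes codes | diabetes codes |
| SAP 8.4 | diabetes codes | diabetes codes |
| SAP Appendix-1 | E10 to E14 | C00 to C97 and D00 to D48, with gaps |
| SAP 10.1.1, propensity covariates | included | not included |

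The label and Appendix-1 point one way and the operational definition points the other. The SAP does not say which governs, and the protocol has no code list that would settle it.

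**2. Consequence if the row is followed literally**

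For each patient, cancer flag = diabetes flag. Any summary that depends only on the flag and the treatment group is then the same for both variables. This covers the counts and percentages, the chi-square test and the standardized difference described in SAP 10.1.5. Matching on a score that contains diabetes tends to bring the diabetes difference towards zero, and the mislabelled line goes with it.

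**3. Which analyses use the variable**

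- Propensity matching (SAP 10.1.1): cancer is not in the covariate list.
- IPTW (SAP 10.1.2): refers back to 10.1.1 for the model, so cancer is not in it either.
- Cox model (SAP 10.1.3): treatment alone, plus components of the score that stay unbalanced. Cancer is not a component and cannot be added by this rule.
- Baseline description and balance check (SAP 8.4, 10.1.4 and 10.1.5): cancer appears here.

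No match, weight or hazard ratio in the disclosed plan therefore depends on this flag.

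**4. How small an imbalance would matter (illustration)**

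The documents give no cancer prevalence. Assume prevalence p1 in one arm and a higher prevalence p2 in the other. The standardized difference is

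d = |p1 − p2| / sqrt{[p1(1 − p1) + p2(1 − p2)] / 2}.

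| p1 (assumed) | d for a 2-point excess | d for a 5-point excess | Excess at which d reaches 0.10 |
|---|---|---|---|
| 10% | 0.064 | 0.152 | 3.20 points |
| 15% | 0.055 | 0.132 | 3.75 points |
| 20% | 0.049 | 0.120 | 4.15 points |
| 25% | 0.046 | 0.112 | 4.45 points |

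Check of the first row: 0.032 / sqrt[(0.0900 + 0.1146) / 2] = 0.032 / 0.3198 = 0.100. Check of the last row: 0.0445 / sqrt[(0.1875 + 0.2078) / 2] = 0.0445 / 0.4446 = 0.100.

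Over this range, a 2-point excess stays within the plan's limit and a 5-point excess breaches it. With the row as written, neither would be seen. If diabetes were equal in both arms, the line would show 0.

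**The case against.** The best defence is that the intention is clear. The row is labelled cancer, Appendix-1 has a cancer list, and a programmer who builds flags from Appendix-1 would get a proper cancer variable. Protocol 7.8 also promises a review of the program code and of descriptive statistics for every variable, and two lines with identical counts in every cohort would be conspicuous. This stands as far as it goes. Duplication is a risk of literal implementation, not a certainty. It does not excuse the text, because code that follows the written definition would agree with its specification.

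A second objection is that correcting the row only makes an imbalance visible. No rule in the plan would act on it, since cancer is not part of the score. That is also true, and it limits what the correction achieves.

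A reader might go further in three ways that the documents do not support:

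- **The treatment comparisons are biased by this error.** They are not, in the disclosed plan, because cancer enters none of the models. Some SAP content is redacted, and whether it uses the variable cannot be checked.
- **The propensity model would be collinear.** This would need cancer to be added to a model that already holds diabetes, and nothing in the visible text plans that.
- **The Appendix-1 list wrongly counts benign growths as cancer.** The list does contain codes between D10 and D36 (D26 is absent), but it gives the cancer codes without descriptions, so the documents do not show that these are out of place. The point can only be a request to confirm the list's scope.

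**Conclusion.** The definition is wrong in Protocol Table 1 and in SAP 8.4, and Appendix-1 of the same SAP shows it to be wrong. If the row is programmed as written, the reported cancer counts, test and standardized difference are those of diabetes, and a true cancer imbalance is not shown. The effect is confined to the baseline description and the balance check.

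The size cannot be derived from the documents. Under assumed prevalences of 10% to 25% in one arm, an excess of roughly 3.2 to 4.5 percentage points in the other is enough to cross the 10% limit unseen. The conclusion assumes that the written row is followed rather than Appendix-1, and that the redacted parts do not use the variable in a model. It is a modest point, but it should be corrected, because the error is unambiguous and the remedy is trivial.

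**What to change.** In Protocol 7.3, Table 1, and in SAP 8.4, replace diabetes mellitus with cancer in the cancer row, and state that the codes are those under Cancer in SAP Appendix-1. Confirm that the codes from D10 to D36 on that list are intended, and remove any that are not. One sentence in SAP 8.4 saying whether cancer is descriptive only would also help, since it is listed there as a covariate but is absent from the propensity list in 10.1.1.

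If programs already exist, compare the cancer and diabetes lines of the baseline table. If they are identical in every cohort, rebuild the cancer flag and rerun that line.

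The cost is one term and one cross-reference in each document, a check of the code list and, at worst, the rerun of one baseline variable. No new data are needed and the disclosed outcome models do not change.
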